### Peripheral Blood Mononuclear Cells (PBMCs)

Correlative Study	Collection Point(s)	SOP for collection	Contact	SOP after collection
Immune Assays	C1D1 prior to treatment  Day 1 of each subsequent cycle  Optional at time of progression	6. One 8-ml BD Vacutainer Cell Preparation Tubes (CPT citrate blue/black tiger top) will be collected from each patient.  7. Immediately after collection, mix the blood sample by gentle inversion several times. The date and exact time of each blood draw should be recorded on the tube.		As soon as possible after the patient is scheduled please send email notification to the [name] lab at [contact] ; [name] at [contact] ; [name] at [contact] ; [name] at [contact] and call the [name] lab at [contact] to arrange for immediate pick-up when the sample is drawn.

*Abbreviated Title: ONC201 in advanced cancers*

*Version Date: 06/17/2020*

## 5.6 SAMPLE STORAGE, TRACKING AND DISPOSITION

Samples collected at NCI will be ordered in CRIS and tracked through a Clinical Trial Data Management system. Should a CRIS screen not be available, the CRIS downtime procedures will be completed and will accompany the specimen and be filed in the medical record. Samples will not be sent outside NIH without appropriate approvals and/or agreements, if required.

At the end of the protocol, samples will be stored for potential further analysis as new information becomes available (only for those subjects who consented to future optional studies). Any new use of identified or coded samples, specimens, or data will undergo prospective and continuing IRB review and approval.

### 5.6.1 Patient sample protections

Each patient sample set will be coded with a unique patient identifier. No patient specific information is encoded in this identifier. The protocol scientific investigators handling samples will be blinded as to as to the patient identification, patient data and outcome. Tissue and blood samples obtained by and stored through WMB will be labeled with unique barcodes.

Blood samples obtained by and stored through the Clinical Pharmacology Core and [name] Lab will be labeled with unique barcodes obtained by [name] laboratory barcode system.

The amount of blood that may be drawn from adult patients (i.e., those persons 18 years of age or older) for research purposes shall not exceed 10.5 mL/kg or 550 mL, whichever is smaller, over any eight week period.

If a patient needs to have a malignant effusion or ascites tapped for diagnostic or therapeutic purposes, a sample will be collected for research.

### 5.6.2 Sample Storage, Tracking and Disposition (CPC)

#### Sample Data Collection:

All samples sent to the Clinical Pharmacology Core (CPC) will be barcoded, with data entered and stored in the Labmatrix system utilized by the CPC. This is a secure program, with access to Labmatrix limited to defined [name] lab personnel, who are issued individual user accounts. Installation of Labmatrix is limited to computers specified by [name]. These computers all have a password restricted login screen.

Labmatrix creates a unique barcode ID for every sample and sample box, which cannot be traced back to patients without Labmatrix access. The data recorded for each sample includes the patient ID, name, trial name/protocol number, time drawn, cycle time point, dose, material type, as well as box and freezer location. Patient demographics associated with the clinical center patient number are provided in the system. For each sample, there are notes associated with the processing method (delay in sample processing, storage conditions on the ward, etc.).

#### Sample Storage and Destruction:

*Abbreviated Title: ONC201 in advanced cancers*

*Version Date: 06/17/2020*

Barcoded samples are stored in barcoded boxes in a locked freezer at either -20° or -80° C according to stability requirements. These freezers are located onsite in the BPC and offsite at NCI Frederick Central Repository Services in Frederick, MD. Visitors to the laboratory are required to be accompanied by laboratory staff at all times.

Access to stored clinical samples is restricted. Samples will be stored until requested by a researcher named on the protocol. All requests are monitored and tracked in Labmatrix. All researchers are required to sign a form stating that the samples are only to be used for research purposes associated with this trial (as per the IRB approved protocol) and that any unused samples must be returned to the BPC. It is the responsibility of the NCI Principal Investigator to ensure that the samples requested are being used in a manner consistent with IRB approval.

Following completion of this study, samples will remain in storage as detailed above. Access to these samples will only be granted following IRB approval of an additional protocol, granting the rights to use the material.

If, at any time, a patient withdraws from the study and does not wish for their existing samples to be utilized, the individual must provide a written request. Following receipt of this request, the samples will be destroyed (or returned to the patient, if so requested) The PI will record any loss or unanticipated destruction of samples as a deviation. Reports will be made per the requirements of section 7.2.

Sample barcodes are linked to patient demographics and limited clinical information. This information will only be provided to investigators listed on this protocol, via registered use of the Labmatrix. It is critical that the sample remains linked to patient information such as race, age, dates of diagnosis and death, and histological information about the tumor, in order to correlate genotype with these variables.

### **5.6.3 Laboratory of [name]**

Samples will be processed immediately by the [name] laboratory. Biospecimens will be collected and processed using validated SOPs that will ensure both specimen quality and patient confidentiality. Using a computerized inventory system and a backup hardcopy process, all specimen collection and processing steps will be documented and the specific location of each specimen will be tracked. Each new specimen collected will be assigned a unique barcode identifier that can be linked to the original specimen collected and other relevant information within the inventory system. Specimen labels will indicate: protocol number, order in which the patient enrolled on the trial, type of sample, collection time, and total volume collected, as appropriate. The inventory process contains other security provisions sufficient to safeguard patient privacy and confidentiality. Access to the inventory system and associated documents will be restricted to appropriate individuals. Requests to use specimens stored in the repository must be approved. SOPs ensure that any changes in informed consent made by a patient and relayed to the PI will be reflected in the inventory system to ensure that specimens are destroyed as appropriate. All laboratory personnel will be trained to adhere to SOPs and will be monitored for high-quality performance.

#### **5.6.4 Procedures for storage of tissue specimens in the Laboratory of Pathology**

Tissues designated for clinical diagnostics are transported to the Laboratory of Pathology (LP) where they are examined grossly and relevant portions are fixed, embedded in paraffin and sectioned and stained for diagnostic interpretation. Unutilized excess tissue that is not placed in paraffin blocks is stored in formalin for up to three months, in accordance with College of American Pathologists/Joint Commission on Accreditation of Healthcare Organizations (CAP/JCAHO) guidelines, and then discarded. Following completion of the diagnostic workup, the slides and tissue blocks are stored indefinitely in the LP's clinical archives. All specimens are catalogued and retrieved utilizing the clinical laboratory information systems, in accordance with CAP/JCAHO regulations. The use of any stored specimens for research purposes is only allowed when the appropriate IRB approval has been obtained. In some cases, this approval has been obtained via the original protocol on which the patient was enrolled.

#### **5.6.5 End of Study**

At the end of the protocol, samples will be stored for potential further analysis as new information becomes available (only for those subjects who consented to future optional studies). Any new use of identified or coded samples, specimens, or data will undergo prospective and continuing IRB review and approval.

The study will remain open so long as sample or data analysis continues. Samples, and associated data, will be stored in the locations listed above until they are no longer of scientific value, or unless the patient withdraws consent for their continued use. If researchers have samples remaining once they have completed all studies associated with the protocol, they must be returned to the WMB laboratory or to the BPC repository. Samples can only be saved at the completion of the study for future use if subjects consented. Access to these samples will only be granted following IRB approval of an additional protocol, granting the rights to use the material.

### **5.7 SAMPLES FOR GENETIC/GENOMIC ANALYSIS**

If not previously evaluated for germline mutations in BRCA1/2 or Lynch syndrome, patients will undergo evaluation upon enrollment on trial. If the research findings are verified in the CLIA certified lab, the subject will be offered the opportunity to come to NIH (at our expense) to have genetic education and counseling with the NCI Genetics Branch to explain this result. If the subject does not want to come to NIH, a referral to a local genetic healthcare provider will be provided (at their expense). This is the only time during the course of the study that incidental findings will be returned. No interrogations regarding clinically actionable findings will be made after the primary analysis.

Subjects will be contacted if a clinically actionable gene variant is discovered. Clinically actionable findings for the purpose of this study are defined as disorders appearing in the American College of Medical Genetics and Genomics recommendations for the return of incidental findings that is current at the time of primary analysis. (A list of current guidelines is maintained on the CCR intranet:

<https://ccrod.cancer.gov/confluence/display/CCRCRO/Incidental+Findings+Lists>). Subjects will

*Abbreviated Title: ONC201 in advanced cancers*  
*Version Date: 06/17/2020*

be contacted at this time with a request to provide a blood sample to be sent to a CLIA certified laboratory which has an FDA approved test for that mutation. If the research findings are verified in the CLIA certified lab, the subject will be referred to the NIH Genetics counseling service for the disclosure of the results.

This is the only time during the course of the study that incidental findings will be returned. No interrogations regarding clinically actionable findings will be made after the primary analysis.

### **5.7.1 Certificate of Confidentiality**

As part of study efforts to provide confidentiality of subject information, this study will obtain a Certificate of Confidentiality which helps to protect personally identifiable research information. The Certificate of Confidentiality allows investigators on this trial to refuse to disclose identifying information related to the research participants, should such disclosure have adverse consequences for subjects or damage their financial standing, employability, insurability or reputation. The informed consent includes the appropriate coverage and restrictions of the Certificate of Confidentiality.

## **6 DATA COLLECTION AND EVALUATION**

### **6.1 DATA COLLECTION**

The PI will be responsible for overseeing entry of data into an in-house password protected electronic system (C3D) and ensuring data accuracy, consistency and timeliness. The principal investigator, associate investigators/research nurses and/or a contracted data manager will assist with the data management efforts. All data obtained during the conduct of the protocol will be kept in secure network drives or in approved alternative sites that comply with NIH security standards. Primary and final analyzed data will have identifiers so that research data can be attributed to an individual human subject participant.

All adverse events, including clinically significant abnormal findings on laboratory evaluations, regardless of severity, will be followed until return to baseline or stabilization of event.

Document AEs from the first study intervention, Study Day 1, through 30 days after the study treatment was last administered. Beyond 30 days after the last intervention, only adverse events which are serious and related to the study intervention need to be recorded.

An abnormal laboratory value will be considered an AE if the laboratory abnormality is characterized by any of the following:

- Results in discontinuation from the study
- Is associated with clinical signs or symptoms
- Requires treatment or any other therapeutic intervention
- Is associated with death or another serious adverse event, including hospitalization.
- Is judged by the Investigator to be of significant clinical impact
- If any abnormal laboratory result is considered clinically significant, the investigator will provide details about the action taken with respect to the test drug and about the patient's outcome.

*Abbreviated Title: ONC201 in advanced cancers*

*Version Date: 06/17/2020*

**End of study procedures:** Data will be stored according to HHS, FDA regulations, and NIH Intramural Records Retention Schedule as applicable.

**Loss or destruction of data:** Should we become aware that a major breach in our plan to protect subject confidentiality and trial data has occurred, this will be reported expeditiously per requirements in section **7.2.1**.

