#### 2.5.2.2 History and Physical, Vital Signs, Height, Weight, and Concomitant Medications

Medical history and physical examination, including vitals signs and concomitant medications, will be conducted at screening and at subsequent visits as indicated in the schedule of assessments. Results of the physical examination including any abnormalities will be documented and can be used for the baseline examination if conducted within 17 days prior to enrolling on trial. Abnormal findings will be reassessed at subsequent visits. On subsequent visits, any newly diagnosed or worsening conditions, signs and symptoms, whether related or unrelated to the trial, will be reported as adverse events.

*Abbreviated Title: ONC201 in advanced cancers*

*Version Date: 06/17/2020*

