## 2.7 SCREEN FAILURES

Screen failures are defined as participants who consent to participate in the clinical trial but are not subsequently assigned to the study intervention or entered in the study. A minimal set of screen failure information is required to ensure transparent reporting of screen failure participants, to meet the Consolidated Standards of Reporting Trials (CONSORT) publishing requirements and to respond to queries from regulatory authorities. Minimal information includes demography, screen failure details, eligibility criteria, and any serious adverse event (SAE).

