### 5.3 TUMOR BIOPSIES

#### 5.3.1 Timing\*

Biopsies will be performed at the following times:

- Mandatory – after consent, prior to treatment on cycle 1 day 1
- Mandatory - cycle 2 day 2 (< 24 hours of ONC201 dose)
- Optional - at the time of progression

\*Biopsies may be not performed on the specific dates and times due to the following reasons, including but not limited to, delayed recovery of hematologic toxicities, delayed clinic schedule, or national holidays.

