### **8.2 ASSESSMENT OF SAFETY EVENTS**

AE information collected will include event description, date of onset, assessment of severity and relationship to study product and alternate etiology (if not related to study product), date of resolution of the event, seriousness and outcome. The assessment of severity and relationship to the study product will be done only by those with the training and authority to make a diagnosis and listed on the Form FDA 1572 as the site principal investigator or sub-investigator. AEs occurring during the collection and reporting period will be documented appropriately regardless of relationship. AEs will be followed through resolution.

SAEs will be:

- Assessed for severity and relationship to study product and alternate etiology (if not related to study product) by a licensed study physician listed on the Form FDA 1572 as the site principal investigator or sub-investigator.
- Recorded on the appropriate SAE report form, the medical record and captured in the clinical database.
- Followed through resolution by a licensed study physician listed on the Form FDA 1572 as the site principal investigator or sub-investigator.

For timeframe of recording adverse events, please refer to section **6.1**. All serious adverse events recorded from the time of first investigational product administration must be reported to the sponsor.

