### 10.3 POPULATIONS FOR ANALYSES

Evaluable for toxicity: All patients will be evaluable for toxicity from the time of their first treatment with ONC201.

Evaluable for objective response: Only those patients who have measurable disease present at baseline, have received at least one cycle of therapy, and have had their disease re-evaluated will be considered evaluable for response. These patients will have their response classified according to the definitions stated below. (Note: Patients who exhibit objective disease progression prior to the end of cycle 1 will also be considered evaluable.)

Evaluable Non-Target Disease Response: Patients who have lesions present at baseline that are evaluable but do not meet the definitions of measurable disease, have received at least one cycle of therapy, and have had their disease re-evaluated will be considered evaluable for non-target disease. The response assessment is based on the presence, absence, or unequivocal progression of the lesions.

Evaluable for Progression Free Survival: In all three cohorts, all participants who took at least one cycle of study drug and have adequate follow-up to be included in a PFS analysis (cohort 1) or to have response and clinical benefit evaluated (cohorts 2 and 3) will be included in the analyses.

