#### 12.5.2.6 Specimen Collection Risks

Risks include those associated with specimen collection including pain, bleeding and the possibility of infection at the sampling site. All care will be taken to minimize risks that may be incurred by tumor sampling. However, there are procedure-related risks (such as bleeding, infection and visceral injury) that will be explained fully during informed consent. If patients suffer any physical injury as a result of the biopsy, immediate medical treatment is available at the NIH's Clinical Center in Bethesda, Maryland. Although no compensation is available, any injury will be fully

*Abbreviated Title: ONC201 in advanced cancers*  
*Version Date: 06/17/2020*

evaluated and treated in keeping with the benefits or care to which patients are entitled under applicable regulations.

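### AE recording (6.1) and SAE sponsor reporting (8.2) start at or about the first dose, so complications of the mandatory pre-treatment research biopsy that arise before it fall outside the stated rules

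*Combined protocol and SAP*

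**What the plan says.** **Start of safety capture.** Section 6.1: "Document AEs from the first study intervention, Study Day 1, through 30 days after the study treatment was last administered". Section 8.2 refers back to 6.1 for the recording period and adds: "All serious adverse events recorded from the time of first investigational product administration must be reported to the sponsor". In the study calendar (3.4) the adverse event row is first marked at Cycle 1 Day 1 and is blank under Screening/Baseline. For the analysis, section 10.3 says: "All patients will be evaluable for toxicity from the time of their first treatment with ONC201".

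**The biopsy.** Section 5.3.1 lists a mandatory biopsy "after consent, prior to treatment on cycle 1 day 1". Sections 2.5.2.8 and 3.1 and calendar footnote 7 also place it before the first dose, and the calendar marks it under Screening/Baseline. Section 12.5.2.6 says of tumor sampling that "there are procedure-related risks (such as bleeding, infection and visceral injury" will be explained at consent.

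**Passages with a different scope.** Section 2.5.2.2 says that at visits after screening "any newly diagnosed or worsening conditions, signs and symptoms, whether related or unrelated to the trial, will be reported as adverse events". Section 2.7, on screen failures, says: "Minimal information includes demography, screen failure details, eligibility criteria, and any serious adverse event (SAE". Section 8.3 requires events meeting the serious criteria to be submitted within 24 hours, and 8.4 requires SAEs in any study subject to be forwarded to the drug supplier within two business days. Neither 8.3 nor 8.4 gives a start date of its own.

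**The concern.** The protocol requires an invasive procedure for correlative research, acknowledges that it can cause serious injury, and performs it before its own AE and SAE rules begin. If a patient bleeds after the biopsy two days before Day 1, recovers and is then treated, neither 6.1 nor 8.2 requires the event to be recorded or sent to the sponsor. If the same patient is never dosed, section 2.7 keeps the SAE. No reason is given for that difference.

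At stake are the count of harm from a protocol-imposed procedure and its prompt arrival at the sponsor. Staff who follow 2.5.2.2 and staff who follow 6.1 could also handle the same event differently.

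**Working it through.** The check is mainly a comparison of passages.

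**Step 1: does the window in 6.1 start at the biopsy or at the first dose?** The wording is loose, since a biopsy could be called an intervention. But the same sentence equates the start with Study Day 1 and counts its 30 days from the last study treatment. Section 2.7 uses the term study intervention for what screen failures are never assigned. Section 8.2 names first product administration, and the calendar row starts at Cycle 1 Day 1. The first dose, or the day of it, is the best-supported reading. If the biopsy was meant, 6.1 and 8.2 would have different starts and would still need reconciling.

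**Step 2: place the biopsy on the timeline.** The order is consent, mandatory biopsy, first ONC201 dose. Section 5.3.1 allows the biopsy on Day 1 itself, and Table 5 labels it as a Cycle 1 Day 1 pre-treatment sample.

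**Step 3: go through the cases.**

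| Biopsy complication | 6.1 recording | 8.2 sponsor reporting | Other passages |
|---|---|---|---|
| Starts and is recognised before Day 1; over by Day 1; patient then treated | Outside | Outside | 2.5.2.2 only if found at an intervening visit |
| Starts and is recognised before Day 1; still present at the Day 1 visit; patient then treated | Onset outside | Onset outside | 2.5.2.2 makes it an AE |
| Biopsy and complication on Day 1, before the dose | Inside | Outside | Calendar marks AEs on Day 1 |
| Starts after the first dose | Inside | Inside if serious | None needed |
| Serious; patient never dosed | No window opens | No window opens | 2.7 keeps the SAE |
| After the Cycle 2 Day 2 biopsy | Inside | Inside if serious | None needed |

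The gap is the first two rows for 6.1 and the first three for 8.2. The second row is the most direct contradiction: the event is an AE under 2.5.2.2, but its onset precedes the window in 6.1.

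**Step 4: bound the size.** The accrual ceiling is 90 (section 10.2), with one pre-treatment biopsy per patient. The documents give no rate of serious biopsy complications, so 1% to 3% is an assumption made here.

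- Lower: 90 × 0.01 = 0.9 events
- Upper: 90 × 0.03 = 2.7 events

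Both figures are upper bounds at their assumed rate. They count every complication as arising before the first dose in a patient who is then treated, whereas complications that begin after the dose are already captured.

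**The case against.** The strongest defence is that a first-dose start is coherent. Section 8.1.1 defines an AE in a subject who has been given a pharmaceutical product, 8.1.5 asks only about relationship to study product, and the safety endpoint is the safety of ONC201. A bleed before any drug is not ONC201 toxicity. This stands for section 10.3, which rightly counts toxicity from first treatment. It does not settle recording and reporting, because the protocol itself imposes the biopsy, and 2.7 already asks for SAEs in people who are never dosed.

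A second defence is that other routes exist. Sections 8.3 and 8.4 set no first-dose limit of their own. Section 7.3 covers deaths within 30 days of a research intervention, other than those due to progression. Section 7.2 relies on policies not reproduced in the documents. A reader might infer from 6.1 and 8.2 that a pre-dose biopsy injury would reach nobody; the documents do not support that. What remains is narrower: 8.2 supplies a start for sponsor reporting that 8.3 and 8.4 leave open, so the passages pull in different directions for a non-fatal event.

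Third, 2.5.2.2 ties its visits to the schedule of assessments, whose AE row starts on Day 1, and 2.7 sets minimal screen-failure data rather than a sponsor-reporting rule. Both points soften the conflict. They do not bring an event that is over before Day 1 into any stated window for a treated patient.

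A reader might also infer that a complication still present on Day 1 would be entered as a baseline symptom and so hide a later AE. Section 2.5.2.2 speaks against this: a condition new since screening is to be reported as an AE, and the review of baseline symptoms in section 2.9 does not override it.

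**Conclusion.** The point holds in a limited form. Biopsy complications that start and are recognised before Day 1 in patients who are then treated are outside the recording window in 6.1 and the sponsor-reporting rule in 8.2. For a biopsy done on Day 1 before dosing, pre-dose complications are outside 8.2 only. Sections 2.5.2.2, 2.7, 8.3 and 8.4 do not share the limit and need to be reconciled with it.

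The conclusion rests on reading the start in 6.1 as the first dose or the day of it. The number of events is small: at most 0.9 to 2.7 among 90 patients at the assumed rates. It would be wrong to infer that all 90 pre-treatment biopsies, with whatever follows them, lie outside the rules, because Day 1 biopsies are within 6.1 and later-onset complications are captured.

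No primary endpoint, early stopping rule or ONC201 toxicity result changes. This is an inexpensive improvement to safety capture and should be made.

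**What to change.** - In 6.1, 8.2 and the calendar AE row, record AEs and report SAEs attributable to protocol-mandated procedures from signed consent. Keep first dose as the start for all other AEs. State that these procedure events count although no drug has yet been given, since 8.1.1 is worded around drug administration.
- Add a procedure-attribution option alongside the study-product relationship in 8.1.5, and on the AE form.
- List pre-dose procedure events separately from the on-treatment toxicity table.
- Make 2.5.2.2 and 2.7 consistent with this start point, and have 8.3 and 8.4 refer to it.
- Leave 10.3 unchanged.

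The cost is wording in these sections, one calendar mark, one form field and a few extra AE entries between consent and Cycle 1 Day 1.
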